1.4 Primary Objectives

- To determine the proportion of high risk smoldering multiple myeloma patients who are progression free at 2 years after receiving Nivolumab and lenalidomide + dexamethasone combination therapy

CONFIDENTIAL

This document is confidential. Do not disclose or use except as authorized.

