5. TREATMENT PLAN

5.1 Treatment Regimen

Treatment will consist of 6 cycles of induction therapy followed by maintenance therapy for a total of 12 months. A treatment cycle is defined as 28 consecutive days.

For treatment cycles 1 through 12, a +/- 7 day window for nivolumab dosing is allowed. For further guidance on lenalidomide and dexamethasone holds and delays, please see Table 17. No investigational or commercial agents or therapies other than those described below may be administered with the intent to treat the participant's malignancy.

** As of September 2017, the trial has been put on partial clinical hold by the Food and Drug Administration: all patients are to discontinue nivolumab indefinitely, and no additional patients will be accrued to the trial. Participants may elect to remain on lenalidomide/dexamethasone or lenalidomide therapy alone for disease control after discussion with the overall PI.

Induction Cycles

Table 7: Nivolumab and Lenalidomide and Dexamethasone Combination (Cycles 1-6)

Agent	Pre-medications/ Precautions	Dose	Route	Schedule	Cycle Length
Nivolumab	None	240 mg	Intravenous	Days 1,15	28 days
Lenalidomide	None	25 mg	Oral	Days 1-21 of each cycle	
Dexamethasone	Take with food; Recommended to be taken in the morning	40 mg	Oral	Days 1, 8, 15	

Maintenance Cycles**

Table 8: Nivolumab and Lenalidomide Combination (Cycles 7-12)

Agent	Pre-medications/ Precautions	Dose	Route	Schedule	Cycle Length
Nivolumab	None	240 mg	Intravenous	Days 1, 15	28 days
Lenalidomide	None	15 mg*	Oral	Days 1-21 of	

CONFIDENTIAL

This document is confidential. Do not disclose or use except as authorized.

				each cycle	
--	--	--	--	------------	--

* If patient was dose reduced during the induction phase for lenalidomide below 15mg, then maintenance phase starts at that dose reduction and not at the higher 15 mg dose.

** During maintenance, if a patient experiences biochemical progression ($\geq 25\%$ increase and an absolute increase of $\geq 0.5\text{g/dL}$ from their nadir in their serum or urine m-spike or FLC with no CRAB features attributable to MM progression) high-dose dexamethasone may be re-added to the combination at a dose of 40mg oral given on days 1, 8, and 15 of a 28 day cycle after discussion with the overall PI.

The participant will be requested to maintain a medication diary. The medication diary should be returned to clinic staff at the end of each cycle.

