5.2.3 Dexamethasone

Dexamethasone will be obtained from commercial supply in this study. This may lead to added costs for the participant or the participant's insurance company.

Dexamethasone will be given as a single oral dose of 40mg on days 1, 8, and 15 of each 28 day cycle during the induction phase of this study (Cycles 1-6 only).

Dexamethasone should be taken at approximately the same time each day. It is recommended that dexamethasone be taken in the morning to reduce insomnia. Each dose should be taken with food. If a dose of dexamethasone is vomited, the participant should continue with the regular schedule of the drug at the next dose. If a dose is missed and less than 12 hours has elapsed since the missed dose, the patient may take the dose for that day. If more than 12 hours has elapsed since missing a dose at the normal time, the patient should not take the dose, but take the next dose at the normal time on the following day. If a dose is missed, it should be taken as soon as possible on the same day. If a dose is vomited, the dose should not be made up and the participant should continue with the regular schedule of the drug at the next dose.. A drug diary must be provided to participants to record oral administration of doses. Dose modification guidelines are described in Section 6.3.

CONFIDENTIAL

This document is confidential. Do not disclose or use except as authorized.

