5.5 Criteria for Taking a Participant Off Protocol Therapy

Patients will be informed that they have the right to withdraw from the study at any time for any reason, without prejudice to their medical care.

In the absence of treatment delays due to adverse event(s), treatment may continue for 12 cycles or until one of the following criteria applies:

- Progression to overt Multiple Myeloma
- Intercurrent illness that prevents further administration of treatment

CONFIDENTIAL

This document is confidential. Do not disclose or use except as authorized.

- Unacceptable adverse event(s)
- Participant demonstrates an inability or unwillingness to comply with the oral medication regimen and/or documentation requirements
- Participant decides to withdraw from the protocol therapy
- General or specific changes in the participant's condition render the participant unacceptable for further treatment in the judgment of the treating investigator

Participants will be removed from the protocol therapy when any of these criteria apply. The reason for removal from protocol therapy, and the date the participant was removed, must be documented in the case report form (CRF). Alternative care options will be discussed with the participant.

A Treatment Ended/Off Study Form will be filled out when a participant is removed from protocol therapy. This form will be provided by the lead site. External sites should submit the form to the Research Project Manager.

In the event of unusual or life-threatening complications, treating investigators must immediately notify the Overall PI, [name] at [contact].

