13. STATISTICAL CONSIDERATIONS

13.1 Study Design/Endpoints

The proportion of patients who achieve progression free at 2 years will be compared to the rate published for the high risk SMM. By the Mayo Clinic model for risk factors, the median time to progression for patients with high risk SMM was only 1.9 years. Therefore, we assume that, a 2-years progression-free rate of 50% will not be considered promising and a true progression free rate of 70% or higher will be considered promising. A single-stage design will be employed with 39 eligible patients entered. If 24 or more of the 39 eligible patients are progression free at 2 years (observed rate of 62%), we will conclude that this treatment warrants further study. The probability of concluding that the treatment is effective if the true rate is 50% is 0.10 and is >0.9 if the true rate is 70%. Assuming a dropout rate of 5%, we will accrue 41 patients to the trial in order to have 39 eligible patients. The Type I and II error probabilities have been derived using exact binomial probabilities.

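### Section 13.1 still turns 24 of 39 into a go conclusion for the planned triplet, although the same version stops nivolumab for every patient

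*Combined protocol and SAP*

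**What the plan says.** - **Objective.** Section 1.4 asks for the proportion "progression free at 2 years after receiving Nivolumab and lenalidomide + dexamethasone combination therapy". Tables 7 and 8 in section 5.1 schedule nivolumab in cycles 1-6 and again in cycles 7-12.
- **Decision rule.** Section 13.1 sets the hypotheses: "a 2-years progression-free rate of 50% will not be considered promising", while "a true progression free rate of 70% or higher will be considered promising". With 24 or more of 39 eligible patients progression-free at 2 years, "we will conclude that this treatment warrants further study".
- **Hold.** Sections 1.1 and 5.1 of the same version say that from September 2017 every patient stops nivolumab indefinitely and nobody else is accrued. They add: "Participants may elect to remain on lenalidomide/dexamethasone or lenalidomide therapy alone for disease control after discussion with the overall PI".
- **Who is analysed.** Section 13.1.1, on the primary endpoint, includes all patients with one dose of study treatment. The sentence names the TTP analysis; I read it as governing the primary rate as well. Sections 1.1, 6.1 and 6.2 let a patient stay on study after one drug is permanently stopped, and list an FDA mandate among the reasons.
- **Length of treatment.** Section 5.5 says "treatment may continue for 12 cycles or until one of the following criteria applies"; sections 1.3 and 5.1 give a total of 12 months.

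Section 13 does not mention the hold.

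**The concern.** The treatment sections were edited for the hold and the inference was not. The cut-off and its error rates were set for one regimen with one planned course of nivolumab. After the hold, the patients counted will have had differing amounts of nivolumab, depending on how long before September 2017 they started. If the rule is met, the plan as written endorses the triplet named in section 1.4.

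That conclusion matters here because section 2.9.1 justifies keeping dexamethasone by the wish to learn what nivolumab adds to the other two drugs. The plan also already accepts the principle at issue: section 13.1.2 adds a 2-year PFS analysis without cyclophosphamide recipients because mobilisation may affect PFS. Stopping the investigational drug for everyone has no corresponding provision.

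**Working it through.** **1. The plan's own figures.** Exact binomial tails for at least 24 successes in 39 (24/39 = 61.5%):
- P(X ≥ 24 | 0.50) = 0.0998, stated as 0.10.
- P(X ≥ 24 | 0.70) = 0.9056, stated as above 0.9.

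Both reproduce. The difficulty is not the arithmetic but the regimen to which the conclusion is attached.

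**2. How much nivolumab could have been lost.** The documents give no first-enrolment date, number enrolled or number still on treatment, so this is an assumed range. Assume uniform accrual over A months ending at the hold, with no stopping for other reasons.
- Planned course: 12 × 28 = 336 days; L = 11.04 months.
- Share completing: max(0, (A − L)/A).
- Mean share of planned nivolumab: A/(2L) if A ≤ L, otherwise 1 − L/(2A).

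| A (months) | Completing 12 cycles | Mean share of planned nivolumab |
|---|---|---|
| 9 | 0% | 9/22.08 = 41% |
| 12 | 0.96/12 = 8% | 1 − 11.04/24 = 54% |
| 15 | 3.96/15 = 26% | 1 − 11.04/30 = 63% |
| 18 | 6.96/18 = 39% | 1 − 11.04/36 = 69% |

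The last row is the full accrual period planned in section 13.2 (1.5 years). Under this model completers reach one half only at A = 2 × 11.04 = 22.08 months.

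**3. The denominator.** Accrual closed at an unstated number. With fewer than 24 treated the rule cannot be met. Requiring 24 successes gives power at 70% of 0.16 for n = 30, 0.65 for n = 35 and 0.86 for n = 38. Applying 61.5% as a proportion instead gives alpha/power of 0.132/0.772 for n = 20 (13 or more), 0.100/0.841 for n = 30 (19 or more) and 0.088/0.865 for n = 35 (22 or more).

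**4. Could the rule be met with little nivolumab?** An illustration from the randomised lenalidomide-dexamethasone trial in section 2.6 (control median 21 months; hazard ratio 0.18, 95% CI 0.09 to 0.32), assuming exponential control times and proportional hazards:
- Control at 24 months: 0.5^(24/21) = 0.453.
- Treated: 0.453^0.18 = 0.87, with 0.453^0.32 = 0.78 and 0.453^0.09 = 0.93 at the interval limits.
- P(X ≥ 24 of 39) is at least 0.993 across that range.

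That trial used different doses and a longer course, so this shows only that passing the cut-off need not reflect nivolumab.

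**The case against.** **The plan already foresees the loss of one drug.** Patients may stay on study after an FDA-mandated stop, the note under Table 11 says that stopping nivolumab need not end protocol therapy, and 13.1.1 keeps everyone dosed. In effect this is a treatment-policy analysis, and it is defensible. That stands. What is missing is the label and the limit on the conclusion: such an analysis estimates the result of starting the triplet under the hold, while 13.1 draws a conclusion about the triplet as planned.

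**Truncation might be thought conservative.** If the rule is met with less nivolumab, the full course should do at least as well. Step 4 shows why this does not follow: the other two drugs could carry the rate over the cut-off by themselves.

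**Stronger readings that the documents do not support.**
- A reader might infer that lenalidomide after the hold has no end. The hold note gives no duration, but the 12-month and 12-cycle limits remain, and remaining on lenalidomide can mean finishing the planned cycles. The documents do not say whether the limit applies.
- A reader might infer that the note contradicts the restriction of dexamethasone to cycles 1-6 in section 5.2.3. The two options match the existing phases, and sections 1.3 and 5.1 already allow dexamethasone to be re-added in maintenance.
- A reader might infer that most patients missed the planned course, or that all were stopped partway. That rests on the assumed accrual period; some may already have finished.
- A reader might infer that 2-year status is sustained by elective lenalidomide. That needs treatment past cycle 12, which no section explicitly authorises, and continued follow-up, which section 5.6 ends at a need for new treatment.

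**Conclusion.** The point holds in this form: section 13.1 attaches an unqualified conclusion about the planned triplet to a 2-year rate that, after the hold, describes starting the triplet with nivolumab stopped early for anyone still on it. This follows from the documents alone. Its size does not: 0% to 39% completing and 41% to 69% mean exposure are conditional on uniform accrual over 9 to 18 months up to the hold and no other stopping. The original error rates are correct for 39 patients on one regimen; the documents do not show that either condition still applies.

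There is a second, smaller gap. The documents do not say whether lenalidomide after the hold is bound by the 12-cycle limit, or whether it counts as protocol therapy or as the new treatment that ends follow-up. The answer determines who is still observed at 2 years.

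**What to change.** Amend sections 13.1 and 13.1.1 before the 2-year results are read, since relabelling afterwards would look data-driven:

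1. Stop using the 24-of-39 cut-off to conclude that the planned triplet warrants further study. Report the 2-year rate with its exact 90% interval and the number treated, as the outcome of starting the triplet with nivolumab stopped by the hold.
2. Add a descriptive table of the rate by time from first dose to the hold date. That grouping is set by the calendar. Do not group by nivolumab cycles received: early progression shortens the count and would create a misleading gradient.
3. Report how many patients continued lenalidomide after cycle 12, where captured, as a count only. Those patients must already have stayed progression-free for about 11 months, so do not compare 2-year status by that use without a landmark.
4. Reconcile the hold notes in sections 1.1 and 5.1 with sections 1.3, 5.5 and 5.6 on whether the 12-cycle limit applies to post-hold lenalidomide, and whether it is protocol therapy or new treatment that ends follow-up.

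**Cost.** The formal go decision for the triplet is given up. Items 1 and 2 need wording and one table from dates on file. Item 3 may need a data field: the follow-up column of the section 10 calendar lists no dosing item, and section 8.2.9 leaves lenalidomide records to institutional policy. No new patients are required.

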13.1.1 Analysis of Primary Endpoint

The primary endpoint will be the 2-year progression-free rate and will be analyzed using binomial probability and corresponding 90% confidence interval. All patients who have received one dose of study treatment will be included for the TTP analysis, including those who die or are lost to follow-up within 2 years.

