1.1 Study Design

This is a phase II study using the combination of Nivolumab and lenalidomide + low dose dexamethasone in patients with high-risk smoldering multiple myeloma. The trial will include a safety run in of 10 patients. If three of the ten patients experience a serious, unexpected adverse event during their first cycle of therapy, the study will be suspended temporarily until further safety review. If any one of the study medications is permanently discontinued for any reason including toxicity, or FDA mandate, the patient may remain on the study at the discretion of the principal investigator.

** As of September 2017, the trial has been put on partial clinical hold by the Food and Drug Administration: all patients are to discontinue nivolumab indefinitely, and no additional patients will be accrued to the trial. Participants may elect to remain on lenalidomide/dexamethasone or lenalidomide therapy alone for disease control after discussion with the overall PI.

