1.2 Number of Patients

A total of 41 patients will be included on this study. Enrollment includes patients who receive the first day of therapy.

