13.1.2 Analysis of Secondary Endpoints

The objective response rate (partial response or better according to the modified IMWG criteria) and the proportion of patients with a MRD, CR, PR or MR will be reported with 90% exact binomial confidence interval (CI). The exact 90% CI around response rate will be no wider than 28% with 39 eligible patients.

Time to progression (TTP) is defined as the time from protocol therapy initiation until documented progression, censored at date last known progression-free for those who have not progressed.

To estimate the duration of response (time from objective response to disease progression or death, or date last known progression-free and alive for those who have not progressed or died), progression-free survival (time

CONFIDENTIAL

This document is confidential. Do not disclose or use except as authorized.

from protocol therapy initiation to the disease progression or death from any cause, censored at date last known progression free for those who have not progressed or died), and overall survival (time from protocol therapy initiation to death or date last known alive), the Kaplan-Meier method will be used.

It is expected that approximately 20% of the patients will receive cyclophosphamide (CTX) for mobilization and this may influence the PFS. Therefore, in a secondary analysis the 2 year PFS rate will be evaluated among those patients who did not receive CTX. Assuming that among the 39 eligible patients between 5-20% of the patients receive CTX for mobilization, the treatment will be considered promising if the observed response rate is at least 62%. With this rule, there is at least 80% probability of concluding the treatment is effective, when the true rate is 70% and less than 10% if true rate is 50%.

Safety analysis will be conducted using the Safety Population defined as any patient receiving one dose of study treatment. For toxicity reporting, all adverse events and laboratory abnormalities will be graded and analyzed using CTCAE version 4 as appropriate.

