13.2 Sample Size, Accrual Rate and Study Duration

A total of 41 patients will be enrolled. We expect 1.5 years of active accrual (approximately 2 patients per month) and 3 years of follow-up of patients.

The final analyses of progression-based endpoints, such as estimating the 2-year progression-free rate and estimating the TTP distribution, will be conducted at the end of the study, which will occur after either all subjects have progressed or died or 2-years after the initiation of therapy of the last subject enrolled, whichever occurs first.

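### The cut-off of 24 is calibrated only for 39 eligible patients: the binomial set is left unclear, no rule covers another n, and the 62% rule in section 13.1.2 misses its stated alpha at n = 32

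*Combined protocol and SAP*

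**What the plan says.** Section 13.1 compares a 2-year progression-free rate of 50% (not promising) with 70% (promising) in a single-stage design using exact binomial probabilities. The rule reads: "If 24 or more of the 39 eligible patients are progression free at 2 years (observed rate of 62" percent), the treatment warrants further study. The stated chance of that conclusion is 0.10 at a true rate of 50% and above 0.9 at 70%. On numbers: "Assuming a dropout rate of 5%, we will accrue 41 patients to the trial in order to have 39 eligible patients".

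Section 13.1.1 analyses the primary endpoint as a binomial proportion with a 90% confidence interval. Its only statement about the analysis set is: "All patients who have received one dose of study treatment will be included for the TTP analysis, including those who die or are lost" (the sentence ends by limiting this to losses before the 2-year mark).

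Section 1.2 adds "Enrollment includes patients who receive the first day of therapy", and section 13.2 "A total of 41 patients will be enrolled", so the planned all-treated set is 41. Section 1.1 records that from September 2017 "no additional patients will be accrued to the trial". The documents do not give the number treated.

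Section 13.1.2 repeats the 2-year analysis in patients who did not receive cyclophosphamide for mobilization, assumed to be 39 less 5-20%. There "the treatment will be considered promising if the observed response rate is at least 62" percent, which in context means the 2-year progression-free rate. It claims at least 80% probability of success at a true rate of 70% and "less than 10% if true rate is 50" percent.

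**The concern.** With a discrete outcome and about 40 patients, moving the denominator by one or two changes the error rates of any cut-off. The plan calibrates one count for one denominator. It then describes a set that may be larger, in a trial whose final denominator was fixed by an accrual stop and not by the design. It also does not say how a patient lost before 2 years counts in the proportion. A time-to-progression analysis can censor such a patient; a binomial must score the patient as a success or a failure.

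At stake is the accuracy of the error rates attached to the go/no-go conclusion, and a stated property of the secondary analysis that is wrong at one n within its own range.

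**Working it through.** **Inputs.** p0 = 0.50, p1 = 0.70, cut-off 24, n = 39 and 5% dropout come from section 13.1. The 41 enrolled come from sections 1.2 and 13.2. The 62% rate and the 5-20% removal come from section 13.1.2.

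**Formula.** P(X >= k | n, p) = sum over x = k to n of C(n,x) p^x (1-p)^(n-x). Alpha uses p = 0.5 and power uses p = 0.7. Pairs below are alpha/power.

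**Step 1, the plan's own figure.** n = 39, k = 24: 0.0998/0.9056. The stated 0.10 and >0.9 reproduce.

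**Step 2, all 41 treated, no losses.**

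| Cut-off of 41 | Alpha | Power |
|---|---|---|
| 24 | 0.174 | 0.959 |
| 25 | 0.1055 | 0.921 |
| 26 | 0.059 | 0.862 |

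No row has alpha at or below 0.10 together with power above 0.9. A search over n = 30 to 41 finds such a cut-off only at n = 39.

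**Step 3, all 41 treated, losses scored as failures.** If exactly two are lost, success needs 24 of the other 39, so 24/41 has the error rates of step 1. If instead each patient has a 5% chance of loss, p becomes 0.5 x 0.95 = 0.475 and 0.7 x 0.95 = 0.665:

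| Cut-off of 41 | Alpha | Power |
|---|---|---|
| 24 | 0.104 | 0.892 |
| 25 | 0.058 | 0.821 |
| 26 | 0.030 | 0.724 |

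**Step 4, the section 13.1.2 claim.** 5% of 39 is 1.95 and 20% is 7.8, so 2 to 8 patients are removed and n = 31 to 37. The literal rule is k = smallest integer at or above 0.62n. The last column is the smallest cut-off with alpha <= 0.10.

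| n | 62% rule | Smallest k with alpha <= 0.10 |
|---|---|---|
| 31 | 20: 0.075/0.808 | 20: 0.075/0.808 |
| 32 | 20: **0.108**/0.867 | 21: 0.055/**0.772** |
| 33 | 21: 0.081/0.839 | 21: 0.081/0.839 |
| 34 | 22: 0.061/0.807 | 22: 0.061/0.807 |
| 35 | 22: 0.088/0.865 | 22: 0.088/0.865 |
| 36 | 23: 0.066/0.837 | 23: 0.066/0.837 |
| 37 | 23: 0.094/0.887 | 23: 0.094/0.887 |

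The 80% power claim holds for the 62% rule at every n here. The alpha claim fails at n = 32 (7 of 39 removed). If 62% stands for 24/39 = 61.5%, the cut-off at n = 34 is 21 and alpha there is 0.115, a second failure. At n = 32 neither 20 nor 21 meets both the 10% and the 80% figures.

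**The case against.** Section 13.1 ties the rule explicitly to 39 eligible patients. The sentence in 13.1.1 literally concerns the TTP analysis, and section 13.2 lists the 2-year rate and the TTP distribution as two separate estimates. On that reading there is no conflict of sets. This stands as a fair reading, so the supportable criticism is ambiguity, not contradiction. It does not settle which n the binomial will have once accrual has stopped, or how losses count.

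The 41 is also just 39 plus the dropout allowance. Step 3 shows that 24/41 keeps the design's error rates if exactly the two expected losses count as failures. That also stands, but the plan does not state this scoring.

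Three stronger inferences are tempting, and the documents do not support them:

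- **That the primary rule never reaches power 0.9.** A literal 62% at n = 39 would need 25 patients (0.054/0.837). But the 62% in section 13.1 is a rounded parenthetical for 24/39; the operative rule is the count, with power 0.906.
- **That alpha is really 0.174.** This needs 24 to be kept as the cut-off in 41 patients with no losses. The plan gives no such rule.
- **That the 62% rule inflates alpha in the primary analysis at smaller n.** Values such as 18/29 (0.133) and 19/30 (0.1002) rest on an assumed n and on carrying a rate that section 13.1.2 uses only for a secondary subset. The second equals 0.10 at the protocol's printed precision.

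**Conclusion.** The concern holds in limited form. The primary design is correctly computed for 24 of 39. What is missing is an unambiguous set for the binomial, a rule for losses, and a cut-off for any n other than 39. If the set is all 41 treated, the nearest cut-offs miss one stated figure each: 25 exceeds alpha by 0.0055, and 26 brings power to 0.862. That is small. The practical weight comes from the accrual stop, because the attained n is not in the documents and 39 cannot be presumed.

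The error in section 13.1.2 does not depend on how 13.1.1 is read: alpha at n = 32 is 0.108 against a stated value below 10%. It affects one n in a range of seven, or two if 62% means 24/39, and only a secondary analysis.

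These figures assume independent patients with a common true rate of 50% or 70%; the 5% loss figures also assume loss unrelated to outcome. The point deserves correction but does not undermine the design.

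**What to change.** In section 13:

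1. Name one set for the binomial. State that patients lost before 2 years count as not progression-free, and say explicitly how deaths without progression count, since section 11.2.4.3 censors them for TTP.
2. Keep 24 if n is 39. Otherwise use the smallest cut-off with exact alpha <= 0.10 at the n analysed. Besides the last column of step 4, this gives 24/38 (0.072/0.863), 25/40 (0.077/0.885) and 26/41 (0.059/0.862). Derive others the same way if fewer were treated.
3. Report the error rates both without loss and with the planned 5% loss scored as failure, for example 26/41: 0.059/0.862 and 0.030/0.724.
4. In section 13.1.2, replace the 62% rate with the exact cut-offs for n = 31 to 37 and restate its figures: alpha below 0.10 throughout, power 0.77 to 0.89 instead of at least 80%.

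A 24-month Kaplan-Meier estimate in all treated patients is an optional sensitivity analysis.

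The cost is wording only, with no new visits or data. The downside is that stated power falls below 0.9 at every n from 30 to 41 except 39, and further once losses count as failures. If the sponsor prefers to protect power at n = 41, 25/41 gives 0.1055/0.921 without loss and 0.058/0.821 with 5% loss; alpha must then be restated as above 0.10.
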